## PROTOCOL SYNOPSIS

Title	A Randomized, Double-Blind, Vehicle-Controlled Study To Evaluate The Safety And Efficacy Of 146-9251 Cream Applied Twice-Daily For Six Weeks In Subjects With Ichthyosis Vulgaris
Study Type	Phase 2
Test Articles	1. 146-9251 Cream (Crown Laboratories) 2. Vehicle Cream
Study Objective	The objective of this study is to determine and compare the safety and efficacy of topical 146-9251 Cream and vehicle cream applied twice daily for up to 6 weeks in subjects with moderate to severe ichthyosis vulgaris (IV).
Study Design	Double-blind, randomized, multicenter, vehicle-controlled study.
Treatment Groups	Eligible subjects will be randomized (1:1) to one of two treatment groups: 1. 146-9251 Cream 2. Vehicle cream The assigned test article will be applied by the subjects twice daily for up to 6 weeks.
Duration of Treatment	Up to 6 weeks
Duration of Study	Up to 6 weeks for an individual subject
Study Population	Male or female subjects at least 12 years of age with moderate to severe IV.
Total Number of Subjects	Approximately 88 subjects will be enrolled (44 per treatment arm).
Number of Sites	Approximately 5 sites will participate in the study.
Inclusion Criteria	To enter the study, a subject must meet the following criteria:  1. Subject is a male or female and is at least 12 years of age at the time of enrollment. 2. Subject has provided written informed consent/assent. A subject under 18 years of age must provide written informed assent and be accompanied by the parent or legal guardian at the time of assent/consent signing. The parent or legal guardian must provide informed consent for the subject. If a subject becomes 18 years of age during the study, the subject must provide written informed consent at that time to continue study participation. 3. Subject and parent/guardian (if applicable) are willing and able to apply the test article(s) as directed, comply with study instructions, and commit to all follow-up visits for the duration of the study. 4. Subject has a clinical diagnosis of IV involving a minimum of 5% body surface area (BSA) within the Treatment Area.  The Treatment Area is defined as the entire body exclusive of the a) head and neck and b) mucosal areas.

 1% BSA is approximately equal to the surface area of the subject's palm and fingers, with the fingers extended yet grouped together, creating a flat oval-like surface area.

	

5. Subject has an Investigator's Global Assessment (IGA) score of at least three (3 = moderate) at the Baseline Visit.

6. Subject is in good general health and free of any disease state or physical condition that might impair evaluation of IV or which, in the investigator's opinion, exposes the subject to an unacceptable risk by study participation.

7. Females must be post-menopausal, surgically sterile, or use an effective method of birth control. Women of childbearing potential (WOCBP) must have a negative urine pregnancy test (UPT) at the Baseline Visit.

Exclusion Criteria	
A subject is ineligible to enter the study if he/she meets one or more of the following criteria:
 

1. Subject is pregnant, lactating, or is planning to become pregnant during the study.

2. Subject is currently enrolled in an investigational drug or device study.

3. Subject has used an investigational drug or investigational device treatment within 30 days prior to first application of the test article.

4. Subject has used any topical therapy, including urea products, topical corticosteroids, or retinoids, in the Treatment Area within 2 weeks prior to the initiation of treatment. Note: a bland emollient may be used in the Treatment Area up to 3 days prior to the initiation of treatment.

5. Subject has used systemic corticosteroids within 4 weeks or retinoids within 24 weeks prior to the initiation of treatment.

6. Subject has stable use of vitamin or herbal supplements for less than 2 weeks prior to the initiation of treatment.

7. Subject has a history of sensitivity to any of the ingredients in the test articles.

8. Subject is known to be noncompliant or is unlikely to comply with the requirements of the study protocol (e.g., due to alcoholism, drug dependency, mental incapacity) in the opinion of the investigator.

9. Subject has a physical condition or other dermatologic disorders (e.g., atopic, seborrheic or contact dermatitis, psoriasis, tinea infections, etc.) which, in the investigator's opinion, might impair evaluation of IV, or which exposes the subject to unacceptable risk by study participation.

Study Procedures	
Subjects can be screened for the study up to 45 days before Visit 1. During screening, the study requirements will be reviewed, written informed consent/assent obtained, and eligibility confirmed. If applicable, the washout from prohibited medications or treatments will be determined and implemented. These procedures may be combined with the Baseline Visit if medication washout is not required. The following procedures will take place according to the visit schedule:

 Defined as amenorrhea greater than 12 consecutive months in women 50 years of age and older.

 Hysterectomy, bilateral tubal ligation (at least six months prior to initiation of treatment), or bilateral oophorectomy.

 Effective forms of birth control include a) hormonal contraceptives [e.g., oral, transdermal, injectable, or vaginal ring] (see footnote 5), b) intrauterine device (IUD) for at least one week prior to test article application, c) barrier methods [condom and spermicidal or diaphragm/cervical cap and spermicidal], d) monogamous relationship with a partner who is sterile [e.g., vasectomy performed at least six months prior to study entry], or e) total abstinence for subjects who are not sexually active. Subjects who become sexually active or begin to have relations with a partner who is not sterile during the study must agree to use an effective form of birth control for the duration of the study.

 WOCBP taking hormonal therapy must be on treatment prior to study entry, continued per label, and must not change their dosing regimen during the study; treatment must be for (1) oral: at least one complete cycle (e.g., four to eight weeks); (2) transdermal, injectable (e.g., Depo-Provera), or vaginal ring (e.g., NuvaRing): at least one week.

 UPT must have a minimum sensitivity of 25 mIU  $\beta$ -hCG/mL.

	
1. Visit 1 (Day 1) - Screening/Baseline Visit: At Visit 1, study staff will explain the study procedures and an informed consent/assent must be signed prior to the initiation of any study-related procedures. At this visit, consenting/assenting subjects will have their medical history and demographics, concomitant medications and procedures/therapies, and inclusion/exclusion (I/E) criteria reviewed to determine subject eligibility. Subjects that require a “washout” period prior to enrollment into the treatment phase to meet I/E criteria requirements will be required to return to the clinic within 45 days to complete the remaining activities. Subjects who require “washout” for longer than 45 days will be re-consented. All WOCBP must have a negative UPT. A brief physical exam, vital signs (including height, and weight), clinical laboratory testing, photography, which is optional, at select site(s) per a photo guide provided by the Sponsor, and clinical evaluations will be performed prior to test article application. The Treatment Area will be defined as the entire body exclusive of a) the head and neck and b) mucosal areas*. The location of the IV to be treated and the percent BSA with IV in the Treatment Area will be recorded prior to test article application. Subjects who meet all inclusion criteria and no exclusion criteria will be randomized and assigned to the next available (lowest) subject number in ascending order. The test article will be weighed prior to dispensing to subjects. Test article, Subject Instruction Sheet, and Subject Diary with completion instructions will be dispensed. At this visit, study personnel will review the Subject Instruction Sheet and the subject and parent/guardian (if applicable) will be instructed on how and where to dispense and apply test article to all affected skin in the Treatment Area and to record applications in the Subject Diary. Subjects will apply the first dose of the assigned test article to all affected skin in the Treatment Area under staff supervision. Any adverse events (AEs) post-application will be recorded. Subjects will apply the assigned test article to all affected skin in the Treatment Area twice daily for up to 6 weeks. The subject will then be scheduled for Visit 2.
 
* Note disease on the neck and face if present may be treated with a bland moisturizer, but shall not be evaluated.
 
2. Visit 2 (Week 2, Day 15 ± 2) and Visit 3 (Week 4, Day 29 ± 2): Subjects enrolled into the study will return to the clinic at Weeks 2 and 4 for the study staff to perform the clinical evaluations, record percent BSA with IV in the Treatment Area, collect, review and dispense a new Subject Diary for test article compliance, update concomitant medications and procedures/therapies, record AEs, collect and weigh used test article and dispense test article if necessary. Photography, which is optional, will be performed at select site(s) per a photo guide provided by the Sponsor. Subjects whose IV is completely clear (IGA score = 0 and all clinical signs of IV = 0 [scaling = 0, fissuring = 0, and erythema = 0]) at Day 15 or Day 29 will complete the end of study (EOS) procedures. These subjects will have completed the study. Subjects whose IV is NOT completely clear will be instructed to continue twice daily treatment until the next visit and to record all applications in the Subject Diary. The subject will be scheduled for the next visit.
 
3. Visit 4 (Week 6, Day 43 ± 3 [OR Day 15 ± 2 or Day 29 ± 2 for subjects who are clear]) – End of Treatment/End of Study or Early Discontinuation: These activities may occur as scheduled at the end of the 43-day treatment period or earlier if (a) the subject is to be dropped from the study or (b) the subject’s IV within the Treatment Area is completely clear at Day 15 or Day 29. At this visit, the study staff will perform the clinical evaluations, record percent BSA

--	---

	
with IV in the Treatment Area, perform clinical laboratory testing, perform photography, which is optional, at select site(s) per a photo guide provided by the Sponsor, update concomitant medications and procedures/therapies, record AEs, collect and review the Subject Diary for test article compliance and collect and weigh used test article. A UPT will be performed on all WOCBP. All subjects will exit the study.

Study Measurements	
At each visit, the skin affected with IV in the Treatment Area defined at the Baseline Visit will be assessed as follows:
 
Efficacy: Investigator’s Global Assessment The IGA score is a static evaluation of the overall or “average” degree of severity of a subject’s disease, taking into account all of the subject’s scaling, erythema, and fissuring in the Treatment Area by the investigator or designee as the subject appears on the day of the evaluation. This evaluation takes into consideration the three individual characteristics of IV (scaling, fissuring, and erythema) as well as hyperpigmentation with the IGA score at each visit representing the average degree of scaling, fissuring, and erythema (<math>\pm</math> hyperpigmentation, if present) that is eligible for treatment. IGA will be assessed using the following 5-point scale: clear (0), almost clear (1), mild (2), moderate (3), or severe (4).
 
Clinical Signs of Ichthyosis Vulgaris Scaling, fissuring, and erythema in the Treatment Area will be graded using the following 5-point scale: clear (0), almost clear (1), mild (2), moderate (3), or severe (4).
 
The degree of hyperpigmentation relative to the subject’s normal skin color associated with the disease affected skin in the Treatment Area will be graded using the following 5-point scale: none (0), minimal (1), mild (2), moderate (3), or severe (4).
 
[REDACTED]
 
[REDACTED]
 
[REDACTED]
 
[REDACTED]
 
[REDACTED]

	
Pruritus At the Baseline Visit, prior to the first application of the test article, the subject's overall experience of pruritus within the previous two weeks will be assessed using a questionnaire (5-D Pruritus Scale). At all follow-up visits, the overall experience of pruritus, in the previous two weeks, will be scored using the same questionnaire. Pruritus assessed by this evaluation should be reported as an AE only if therapy is required.
 
Percent Body Surface Area with Active Ichthyosis Vulgaris in the Treatment Area The percent BSA with active IV within the designated Treatment Area will be calculated at Baseline and at all follow-up visits.
 
Safety: Test Article Compliance Subjects will apply the first dose of test article to skin affected with IV within the Treatment Area under staff supervision. Subjects will be instructed to record the date and time that each dose was applied. At each visit, subject diaries will be reviewed and subjects will be counseled regarding compliance, if necessary. All dispensed test article will be weighed at each visit and will be recorded.
 
Adverse Events All AEs will be recorded. At each visit after the Baseline Visit/Day 1, subjects will also be questioned specifically about the status of any ongoing AEs.
 
Clinical Laboratory Testing and Pregnancy Testing Chemistries, hematology, and urinalysis and UPTs will be performed at Baseline and EOS.

Study Endpoints	
Efficacy Endpoint(s): IGA scores and the clinical signs and symptoms of IV will be dichotomized to "treatment success" or "treatment failure" where "treatment success" is defined as at least a two grade decrease in severity score relative to Baseline. Dichotomization of scores for clinical signs and symptoms of IV will exclude subjects with Baseline scores of 0 or 1 unless the corresponding sign score at follow-up visits is >1.
 
The primary efficacy endpoint will be the proportion of subjects with IGA "treatment success" at EOS, where EOS is the subjects last completed post-Baseline visit.
 
Secondary efficacy endpoints (observed data only) include:
 

• The proportion of subjects with IGA "treatment success" at Days 15 and 29.

• The proportion of subjects with a IGA score of 0 or 1 representing "cleared" or "almost cleared" at EOS.

• The proportion of subjects rated "treatment success" for each of the clinical signs and symptoms of IV at Days 15, 29, and EOS.

• Changes in percent BSA with IV in the Treatment Area at Days 15, 29, and EOS relative to Baseline.

• Change from Baseline in 5-D pruritus score at Days 15, 29, and EOS.

• Changes in [REDACTED] at Days 15, 29, and EOS relative to Baseline.

	
Safety Endpoint(s):          Safety endpoints will include assessment of UPT (as applicable), clinical laboratory testing, and AEs, including serious adverse events (SAEs).

Sample Size Calculations
	
No formal power calculations were conducted to establish sample size. The sample size was selected empirically to enable sample size calculations for future pivotal studies.


Statistical Methods
	
All statistical analyses and summaries will be prepared using SAS® unless otherwise stated. All subjects enrolled in the study who were dispensed and applied test article at least once will be included in the analysis of safety and will be considered the Safety population. All randomized subjects who were dispensed the test article will be considered the intent-to-treat (ITT) population. The per-protocol (PP) population will be a subset of the ITT population consisting of subjects who have completed the study without significant protocol deviations. The statistical analysis plan will provide details regarding inclusion in the PP population. Missing values for the IGA score at EOS in the ITT population will correspond to IGA “treatment failure”. All other analyses for both ITT and PP populations will use observed data only. Efficacy analyses will be performed on both the ITT and PP populations with the ITT population considered primary.
 
Demographic and baseline characteristics will be summarized by treatment group for the Safety, ITT, and PP populations. Frequency counts and percentages will be reported for categorical data and sample size, mean, median, standard deviation (SD), minimum and maximum will be reported for the continuous variables.
 
Efficacy Analyses:          For each of the efficacy endpoints (IGA and signs of IV), the following summaries will be prepared at Days 15, 29, and EOS:
 
 
• Frequency distribution of observed scores
 
• Frequency distribution of change from Baseline
 
• Shift tables for changes from Baseline to Visits 2, 3, and 4
 
• Frequency distribution of treatment success rates
 
 
At EOS, 95% confidence intervals will be calculated for the difference in proportions between treatment groups for rates of treatment success. The treatment groups will be compared with respect to “treatment success” rates for IGA and each sign of IV using Fisher’s Exact Test. The proportion of subjects with an IGA score of 0 or 1 will be analyzed likewise using Fisher’s Exact Test.
 
Descriptive statistics (including mean, median, SD, minimum, and maximum) for observed and change from Baseline values in the percent BSA affected in the Treatment Area at each visit will be presented.
 
For 5-D pruritus score and [REDACTED], descriptive statistics for observed and change from baseline values will be provided by treatment group at Baseline and at Days 15, 29, and EOS. The treatment groups will be compared with respect to the change from Baseline using mixed model of repeated measures (MMRM) including terms for treatment, visit, treatment by visit interaction, and the Baseline value serving as the covariate.


 Subjects with Baseline scores of 0 or 1 will be excluded from summaries and analyses of success rates unless the corresponding sign score at follow-up visits is >1.

	
Safety Analyses:
 
Dosing Compliance Descriptive statistics will be used to summarize test article compliance for the ITT population. Measures of test article compliance will include the duration of treatment (number of days dosed), the total number of applications (determined from the actual number of applications reported by the subject), and the percent of expected doses applied. A subject will be considered compliant with the dosing regimen if the subject applies at least 80% but no more than 120% of the expected number of applications.
 
Extent of Exposure The total amount of test article used (grams of test article applied) will be calculated from the weights of the returned test articles. Descriptive statistics (mean, median, SD, minimum and maximum) will be determined for the total amount of test article used by each subject by treatment group.
 
Clinical Laboratory Testing, and Urine Pregnancy Testing A listing of the clinical laboratory results and UPT results will also be prepared.
 
Adverse Events All AEs reported during the study will be listed, documenting onset, whether therapy was required, any change in test article dosing, severity, possible relationship to test article, and outcome. Verbatim terms on the case report forms (CRFs) will be linked to preferred terms (PTs) and system organ class (SOC) using the Medical Dictionary for Regulatory Activities (MedDRA) mapping system. All reported AEs will be summarized by the number of subjects reporting AEs, SOC, PT, severity, and relationship to test article by treatment group.

--	--

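### The observed-only rule drops Day 15 clear exits from the Day 29 success rates, so in any arm with such exits and a non-success the rate falls below response achieved by Day 29

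*Combined protocol and SAP*

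**What the plan says.** All references are to the Protocol Synopsis.

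- **Exit rule** (Study Procedures, Visits 2 and 3). A subject is completely clear when "IGA score = 0 and all clinical signs of IV = 0 [scaling = 0, fissuring = 0, and erythema = 0". Subjects who meet this "at Day 15 or Day 29 will complete the end of study (EOS) procedures. These subjects will have completed the study". Only those who are not clear go on to the next visit.
- **Label of the exit visit** (Study Procedures, Visit 4). Visit 4 falls at "Day 43 ± 3 [OR Day 15 ± 2 or Day 29 ± 2 for subjects who are clear", so an early clear exit is recorded as Visit 4/EOS.
- **Data rule** (Study Endpoints). IGA success and sign success at Day 29 are listed under "Secondary efficacy endpoints (observed data only) include". Statistical Methods first sets a failure rule for missing EOS IGA in the ITT population, then adds: "All other analyses for both ITT and PP populations will use observed data only".
- **EOS** (Study Endpoints). The primary endpoint is read at EOS, "where EOS is the subjects last completed post-Baseline visit".
- **Success and entry severity.** Success is a fall of two or more grades from Baseline (Study Endpoints). Inclusion criterion 5 requires an "IGA) score of at least three (3 = moderate) at the Baseline Visit".
- **Signs.** Success rates leave out Baseline sign scores of 0 or 1 unless the follow-up score exceeds 1 (Study Endpoints and footnote 7).

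**The concern.** A subject who clears fully by Day 15 has the best outcome the scale allows, and that outcome is why no Day 29 value exists. Under the observed-only rule the subject simply leaves the Day 29 table. The text reviewed makes no exception for clear exits.

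Day 15, Day 29 and EOS summaries are planned for the same endpoints, so they will be read as a sequence. If exit assessments are also tabulated at Day 15, the sequence can dip at Day 29 only because early responders have left. The Day 29 comparison between arms also depends on how the exits split between them.

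**Working it through.** The plan gives no clearance rate, expected success rate or power calculation, so there is no planned figure to reproduce. The direction follows from the rules. The sizes below are illustrations.

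**Step 1: every Day 15 clear exit is an IGA success.** Baseline is at least 3 and exit is 0, so the fall is at least 3 grades against the 2 required. For scaling, fissuring and erythema the exit score is also 0. A Baseline score of 2 or more therefore gives a sign success, and a clear exit with Baseline 0 or 1 is already excluded for that sign.

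**Step 2: direction within an arm.** Take 44 per arm (Total Number of Subjects) and assume no other missing data. Let c be the Day 15 clear exits and S the subjects who are in success at Day 29 or exited clear at Day 15.

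- Response achieved by Day 29: S/44
- Observed-only Day 29 rate: (S − c)/(44 − c)
- Difference: S/44 − (S − c)/(44 − c) = c(44 − S) / [44(44 − c)]

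This is above zero whenever c > 0 and S < 44. The same algebra applies to the three signs, with the number evaluable in place of 44. Assumed example for scaling: 40 evaluable, 20 successes, 4 clear exits; 20/40 = 50.0% becomes 16/36 = 44.4%.

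**Step 3: between-arm difference.** Assume S = 22 on active and 11 on vehicle. The p-values are two-sided Fisher tests; the plan states no sidedness.

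| Clear exits, active/vehicle | Active | Vehicle | Difference (points) | p |
|---|---|---|---|---|
| 0/0 | 22/44 = 50.0% | 11/44 = 25.0% | 25.0 | 0.027 |
| 6/1 | 16/38 = 42.1% | 10/43 = 23.3% | 18.8 | 0.096 |
| 3/3 | 19/41 = 46.3% | 8/41 = 19.5% | 26.8 | 0.018 |

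The first row is also the response-by-Day-29 result in all three cases.

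**Step 4: where the difference does not move.** Setting the two within-arm drops equal gives 22·cA/(44 − cA) = 33·cV/(44 − cV), that is cA/(44 − cA) = 1.5·cV/(44 − cV). For cV = 1, 2, 3 and 4 this gives cA = 1.5, 2.9, 4.4 and 5.7. With more active exits than this the difference shrinks; with fewer it widens.

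**Step 5: a dip with no loss of response.** Assume 20/44 = 45.5% in success at Day 15, 6 of them clear exits who are tabulated at Day 15. Nobody seen later loses success and 2 more respond. Observed-only Day 29 is (20 − 6 + 2)/(44 − 6) = 16/38 = 42.1%. Response achieved by Day 29 is 22/44 = 50.0%.

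**The case against.** The strongest reply is that observed-only is a rule, stated twice and chosen on purpose, and that S/44 is a different quantity. The plan asks for success at Day 29. Adding known earlier successes to a rate below 100% must raise it, which does not show that the planned figure misstates Day 29 status. Relapse makes this concrete. With 22/44 and 6 clear exits, true Day 29 status would be 47.7%, 45.5%, 43.2% or 40.9% if 1, 2, 3 or 4 of the 6 lost success. The response-by-Day-29 row (50.0%) is closer for 0 or 1 relapses, and the observed-only row (42.1%) is closer for 2, 3 or 4. No data after exit can settle which applies.

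This stands. It is why the observed-only row should stay and the added row must not be called Day 29 status. It does not remove the point: the planned rate describes only subjects who had not cleared by Day 15, and nothing in the planned table says so.

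A reader might infer more than the documents support:

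- *That the plan has no rule for Day 29.* It has one, observed data only; what it lacks is an exception for clear exits.
- *That the Day 29 treatment effect is understated.* The 3/3 case widens it.
- *That Day 15 is certainly safe.* The exit visit is labelled Visit 4 and the shift tables are indexed by visit number, so keeping these subjects at Day 15 is a reasonable inference, not stated text.
- *That hyperpigmentation success is lowered too.* It is graded on its own scale ("associated with the disease affected skin in the Treatment Area will be graded using the following 5-point scale: none (0") and need not be 0 at exit, so its direction is not fixed. Whether it is analysed as a success endpoint at all is not clear.

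**Conclusion.** The point holds as a minor reporting weakness. In any arm with at least one Day 15 clear exit and at least one non-success, the observed-only Day 29 IGA success rate is below the rate of response achieved by Day 29. The same holds for scaling, fissuring and erythema among subjects with a Baseline score of 2 or more. That direction needs no clinical assumption.

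The size is unknown, and zero if nobody clears by Day 15. In the assumed cases the difference moves from 25.0 points by −6.2 (6/1) or +1.8 (3/3). For scale, the standard error of a 50% v 25% difference is sqrt(0.25/44 + 0.1875/44) = 10.0 points. The p-values matter only if Fisher's test is run at Day 29; Efficacy Analyses names no visit for it.

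A reader might take this as a threat to the main result. It is not: the EOS definition keeps clear exits in the primary and other EOS endpoints, confidence intervals are planned only at EOS, and no decision rule is attached to Day 29. Day 15 is unaffected only if the exit assessment is also tabulated there.

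The conclusion rests on the synopsis and schedule of events. Statistical Methods refers to a statistical analysis plan for per-protocol inclusion details, and no Day 29 exception appears in the text reviewed.

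**What to change.** Before unblinding, add to the analysis plan:

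1. Tabulate each clear-exit assessment at the study day on which it occurred (Day 15 or Day 29) as well as at EOS.
2. For IGA, scaling, fissuring and erythema, add a Day 29 row: success at Day 29, or at the Day 15 exit visit for subjects who exited completely clear. Label it response achieved by Day 29. Keep the existing exclusion for Baseline sign scores of 0 or 1.
3. Keep the observed-only row beside it with equal prominence.
4. Footnote the number of Day 15 clear exits per arm under every Day 29 table, including shift tables, percent BSA and 5-D pruritus.
5. If hyperpigmentation is analysed as a success endpoint, use its actual exit score.

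The cost is a short derivation rule, one extra row per endpoint and a footnote, with no new visits or data. The exit rule and the MMRM are left as they are. The downside belongs in the table notes: the added row mixes Day 15 and Day 29 assessments, and it overstates Day 29 status if cleared subjects relapse after exit, which cannot be checked.

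### Each 0–4 clinical sign is compared between arms only as a two-grade-drop yes/no; a prespecified supportive ordinal comparison should be added beside the Fisher test

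*Combined protocol and SAP*

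**What the plan says.** All references are to the Protocol Synopsis.

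- **Scale** (Study Measurements, Clinical Signs): "Scaling, fissuring, and erythema in the Treatment Area will be graded using the following 5-point scale", running from clear (0) to severe (4). Hyperpigmentation has its own five-grade scale under the same heading.
- **Success** (Study Endpoints), for the IGA and the signs alike: "is defined as at least a two grade decrease in severity score relative to Baseline".
- **Who is left out** (Study Endpoints; repeated in footnote 7): "Dichotomization of scores for clinical signs and symptoms of IV will exclude subjects with Baseline scores of 0 or 1". They come back in only when the sign is above 1 at follow-up. A sign that starts at 2 is always analysed.
- **Entry floor** (Inclusion Criteria, item 5): an IGA "score of at least three (3 = moderate) at the Baseline Visit". No floor is set for an individual sign.
- **Test** (Statistical Methods, Efficacy Analyses): "The treatment groups will be compared with respect to “treatment success” rates for IGA and each sign of IV using Fisher’s Exact Test". A 95% confidence interval for the difference in success rates is added at EOS.
- **Use of the full scale** (same section): descriptive only, through distributions of scores and of changes, and "Shift tables for changes from Baseline to Visits 2, 3, and 4".
- **Contrast** (same section): the 5-D pruritus score, also secondary, is compared between arms on its full scale in an MMRM with the Baseline value as covariate. No reason is given for treating the signs differently.

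Sign success is a secondary endpoint. No power calculation was done, and the sample size was chosen to inform later pivotal studies.

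**The concern.** The sign endpoints are where the trial would show which component of the disease the cream improves. The two-grade cut makes the answer depend on where the sign starts. A severe sign succeeds by reaching mild, but a mild sign must vanish. In a sign that starts at 2, a fall to 1 and a rise to 4 are the same result to the planned test.

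If the cream acts mainly by moving many subjects one grade, the shift tables would show it, but no planned estimate or test would compare the arms on it. Component-level effects are part of what a study meant to inform pivotal trials should deliver. An ordinal analysis chosen after unblinding would carry less weight than one named now.

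**Working it through.** The plan states no power, so there is no figure to reproduce.

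**1. What counts as success.** Success requires follow-up ≤ Baseline − 2.

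| Baseline sign | Highest follow-up grade that succeeds |
|---|---|
| 4 | 2 |
| 3 | 1 |
| 2 | 0 |
| 0 or 1 | none possible |

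**2. Inputs.** From the documents: about 44 per arm, 1:1 allocation. Assumed: two-sided 5% (in line with the 95% intervals), no dropout, vehicle rates, Baseline mix and effect size. Fewer subjects per sign will be analysable after the Baseline exclusion; 25 per arm stands in for that.

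**3. Worked case: every subject starts at 2, common shift.** Suppose 40% of vehicle subjects do not improve, 40% fall one grade and 20% clear. A common odds ratio multiplies each cumulative odds. With an odds ratio of 3 (log 3 = 1.10):

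- Clearing: vehicle odds 0.20/0.80 = 0.25; active 0.75; active rate 0.75/1.75 = 43%.
- Any fall: vehicle odds 0.60/0.40 = 1.5; active 4.5; active rate 4.5/5.5 = 82%.

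Simulated power (4,000 runs), Fisher on success against Wilcoxon on the change score, odds ratio 3. Gains are computed before rounding.

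| Vehicle: no fall / one grade / clears | Per arm | Fisher % | Wilcoxon % | Gain (points) |
|---|---|---|---|---|
| 40 / 40 / 20 | 44 | 56.6 | 77.4 | 20.8 |
| 40 / 40 / 20 | 25 | 31.0 | 53.9 | 22.8 |
| 30 / 40 / 30 | 44 | 61.2 | 76.9 | 15.7 |
| 20 / 40 / 40 | 44 | 62.2 | 75.4 | 13.3 |
| 15 / 35 / 50 | 44 | 60.5 | 69.8 | 9.3 |

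Over odds ratios 2 to 4 the gain runs from 6.5 to 23 points. At odds ratios 6 to 8 it falls to between 0.6 and 12, because both tests are then strong. With only 10% clearing on vehicle, a formula-based comparison at odds ratio 3 and 44 per arm gives 35% for Fisher against 78% for an ordinal analysis, a gap of 43 points.

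**4. How much is the cut and how much is Fisher.** A parallel run at 20% vehicle clearance, 44 per arm and log odds ratio 1.1 gave Fisher 57%, uncorrected chi-square 67% and Wilcoxon 80%. Of the 80 − 57 = 23 points, 67 − 57 = 10 come from Fisher's conservatism and 80 − 67 = 13 from using the scale.

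**5. Mixed Baseline grades.** Here a Baseline-stratified rank test is set against the two success tests in subjects starting at 2 or more, at log odds ratio 1.1. The labels and mixes are assumptions.

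| Assumed Baseline mix, grades 0/1/2/3/4 (%) | Fisher % | Chi-square % | Stratified rank % |
|---|---|---|---|
| Scaling-like 0/0/10/60/30 | 56 | 64 | 80 |
| Mostly 2–3: 0/10/50/35/5 | 45 | 50 | 74 |
| Fissuring-like 20/20/30/20/10 (0.60 × 88 ≈ 53 subjects) | 29 | 36 | 54 |
| Erythema-like 30/30/25/10/5 (0.40 × 88 ≈ 35 subjects) | 18 | 24 | 38 |

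The gains over Fisher are 24, 29, 25 and 20 points. A separate simulation at the same effect size, with other assumed vehicle rates, put the range at 6 to 38.

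**6. When the benefit comes as large falls only.** Keep vehicle at 40/40/20 with 44 per arm.

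- Active 40/15/45 (no more subjects improve, but more of those who do clear): Fisher 64%, Wilcoxon 26%. Fisher leads by 38 points.
- Active 30/25/45: Fisher 64%, Wilcoxon 52%. Fisher leads by 12 points.

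Across the scenarios of this kind that were examined, Fisher led by about 7 to 41 points.

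**The case against.** The strongest reply is that no power loss can be read off the plan, and this stands. The documents give no rates, effect size or Baseline mix, and a proportional shift is the model that favours a rank test. Step 6 shows the opposite result under a different pattern of benefit. A reader might infer that the cut costs each sign a fixed number of points, or that the success test should be replaced. The documents support neither.

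The assumed mixes are also open to challenge. The means of the scaling-, fissuring- and erythema-like mixes are 3.2, 1.8 and 1.3, which average 6.3/3 = 2.1. Entry requires an IGA of at least 3, and the IGA is described as reflecting the average degree of those signs. The synopsis does not make it a strict arithmetic mean, so mild individual signs remain possible. Nothing says how common they are, or that fissuring and erythema are the signs that start mild.

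The simulations also leave out subjects starting at 0 or 1 whom the plan brings back when the follow-up sign exceeds 1. They cannot fall two grades, so they enter only as failures. The Fisher figures are therefore close to, but not exactly, the planned analysis.

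Finally, the full scale is reported: a move from 2 to 1 will be visible in the shift tables. That is true, but a table is not a between-arm comparison. The secondary status of these endpoints limits the stakes without answering the point.

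**Conclusion.** The structural point holds from the text alone. Each sign is compared between arms only on a two-grade fall, a sign starting at 2 must clear to count, and one-grade changes are described without being compared.

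The size is conditional. Under a common shift at log odds ratio 1.1, a Baseline-stratified ordinal test gains roughly 6 to 38 points over the planned Fisher test, partly because Fisher is conservative at this size. Vehicle rates, Baseline mixes and effect are all assumed, and the sign of the difference reverses if benefit comes only as falls of two or more grades.

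A reader might go further and infer that a real improvement in fissuring or erythema would probably be reported as no difference, and that an ordinal test would cure this. The documents do not show how those signs start. Even in the assumed mixes the ordinal test reaches only 54% and 38%, so power stays low for signs that few subjects have at Baseline.

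This is a cheap improvement to secondary analyses. It does not touch the primary IGA endpoint.

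**What to change.** In Statistical Methods, Efficacy Analyses:

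- Keep Fisher's exact test and the 95% confidence interval on sign success as the named secondary analysis.
- Add a prespecified supportive between-arm comparison at EOS of the full 0–4 score for scaling, fissuring, erythema and hyperpigmentation. Use either a van Elteren test stratified by Baseline sign score, or a proportional-odds model with Baseline sign score as covariate. Choose one before unblinding.
- Report the common odds ratio with its 95% CI for each sign. If the van Elteren test is chosen, take the estimate from the proportional-odds model.
- State which subjects enter. A comparison adjusted for Baseline grade does not need a rule that readmits subjects according to their follow-up score.
- Label the results supportive.

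**Cost.** A few lines of text and one analysis per sign; the Schedule of Events already collects the scores at every visit. The downsides are one more secondary test per sign, with no multiplicity control stated, and an odds ratio that is less direct to read than a success rate. Keeping the success rates beside it meets the second, and also keeps a benefit made up of large falls visible.
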